Occurrence of an immune-related adverse event is an anticipated risk in participants treated with immune-oncology drugs such as sabatolimab. In the case of an immune-related event, there are dose modification and management guidelines, including detailed plans for follow-up of toxicities. In addition, the protocol references and will adhere to recent American Society of Clinical Oncology (ASCO) practices guidelines for management of immune-related adverse events in participants treated with checkpoint inhibitors (Brahmer et al 2018) (see Section 6.5.3 and Section 6.5.4.1).

Based on currently available data, there are no known significant overlapping toxicities between the combination of venetoclax and azacitidine and sabatolimab. However, this novel combination treatment may have unforeseen risks, which could be serious. In particular, there is the potential for increased toxicity secondary to cytokine release syndrome due to activation of T cells and macrophages, and there may also be changes in immune function that could lead to autoimmunity or other immune-related adverse events as well as increased risk of infection. All participants enrolled will be monitored closely for these potential toxicities.

Furthermore, as the safety of sabatolimab administered in combination with azacitidine + venetoclax has not been assessed previously, the protocol stipulates that consecutive Safety runin cohorts at 400 mg Q4W and 800 mg Q4W (Part 1) will be observed for at least 2 treatment cycles followed by a Safety Review Meeting, before opening enrollment to a larger participant population in Part 2 (Expansion). A Steering Committee (see Section 10.2.2) will review the safety data during the course of the study including at the time of the two safety reviews planned during the Safety run-in. Women of childbearing potential and sexually active males must be informed that taking the study treatment may involve unknown risks to the fetus if pregnancy were to occur during the study, and agree that in order to participate in the study they must adhere to the contraception requirements outlined in the exclusion criteria until at least 30 days after the last dose of venetoclax, 90 days after the last dose of azacitidine, and 150 days after the last dose of sabatolimab, whichever is later. If there is any question that the participant will not reliably comply, they should not be entered or continue in the study.

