13. Participants with prior malignancy, except:

a) Participants with history of intermediate risk MDS or lower risk MDS treated by any supportive care (e.g. growth factors, TGF'beta agents) or untreated are eligible

b) Participants with history of intermediate or lower risk MDS who were treated adequately with lenalidomide and then failed are eligible

c) Participants with history of adequately treated malignancy for whom no systemic anti cancer therapy (namely chemotherapy, radiotherapy or surgery) is ongoing or required during the course of the study. Subjects who are receiving adjuvant therapy such as hormone therapy are eligible. However, subjects who developed therapy-related MDS are not eligible (see exclusion criterion 9).

14. Cardiac or cardiac repolarization abnormality, including but not limited to any of the following:

a) History of myocardial infarction (MI), angina pectoris, or coronary artery bypass graft (CABG) within 6 months prior to starting study treatment

b) QTcF > 470 ms at screening, long QT syndrome or family history of unexplained cardiac death

c) Clinically significant cardiac arrhythmias (e.g., ventricular tachycardia), complete left bundle branch block, high-grade AV block (e.g., bifascicular block, Mobitz type II and third degree AV block)

15. Sexually active males unless they use a condom during intercourse while taking azacitidine and for 3 months after stopping the drug. They should not father a child in this period. A condom is required to be used also by vasectomized men in order to prevent delivery of the drug via seminal fluid.

In addition, male participants must not donate sperm for the time period specified above.

- 16. Participant is pregnant or breastfeeding
- 17. Women of childbearing potential, defined as all women physiologically capable of becoming pregnant, unless they are using highly effective methods of contraception during study treatment and for at least one month after the last dose of venetoclax, 3 months after the last dose of azacitidine (or as per their respective local labels, whichever is longer) and 150 days after the last dose of sabatolimab. Highly effective contraception methods include:
 - Total abstinence (when this is in line with the preferred and usual lifestyle of the participant). Periodic abstinence (e.g. calendar, ovulation, symptothermal, post-ovulation methods) and withdrawal are not acceptable methods of contraception

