8.4.3 Pregnancy and assessments of fertility

Medical documentation of oophorectomy, hysterectomy, or tubal ligation must be retained as source documents. Subsequent hormone level assessment to confirm the woman is not of child-bearing potential must also be available as source documentation in the following cases:

- 1. Surgical bilateral oophorectomy without a hysterectomy
- 2. Reported 12 months of natural (spontaneous) amenorrhea with an appropriate clinical profile.

In the absence of the above medical documentation, FSH testing is required of any female participant regardless of reported reproductive/menopausal status at screening/baseline.

All pre-menopausal women who are not surgically sterile will have pregnancy testing. Additional pregnancy testing might be performed if requested by local requirements.

At screening, a serum pregnancy test (serum β -HCG) must be performed within 3 days (72 hours) before the first dose.

During the study, a urine/serum pregnancy test should be performed at Day 1 of each cycle (except Cycle 1 if a pregnancy test had been performed within 72 hours of the first dose) and a serum pregnancy test at EOT visit. Pregnancy testing (urine/serum) should occur at monthly intervals during the 150-day safety follow-up period. Refer to Table 8-1 for pregnancy testing schedule.

A positive urine pregnancy needs to be confirmed with a serum test. Confirmed positive pregnancy test requires immediate discontinuation of study treatment and discontinuation from study. See Section 10.1.4 for pregnancy reporting.

The pregnancy tests will be recorded only in the source documentation, not in the CRF.

Women of childbearing potential should employ the use of highly effective contraception during study treatment, for 90 days after the last dose of azacitidine, 30 days after the last dose of venetoclax (or as per their respective local labels, whichever is longer) and 150 days after the last dose of sabatolimab. Highly effective contraception methods are defined in Section 5.2.

A condom is required for all sexually active male participants to prevent them from fathering a child AND to prevent delivery of study treatment via seminal fluid to their partner while taking azacitidine and for 3 months after stopping this drug. In addition, male participants should not donate sperm for the time period specified above.

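### The protocol gives sexually active men two different contraception end dates (Section 4.6 against criterion 15 and Section 8.4.3) and does not say which prevails

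*Protocol*

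**What the plan says.** **Section 4.6 (Risks and benefits).** The paragraph opens "Women of childbearing potential and sexually active males must be informed" of possible fetal risk. It then makes it a condition of participation that "they must adhere to the contraception requirements outlined in the exclusion criteria until at least 30 days after the last dose of venetoclax". The azacitidine period in the same sentence is 90 days, and the sentence closes with "and 150 days after the last dose of sabatolimab, whichever is later". Both sexes are covered together.

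**Section 5.2, criterion 15 (men).** Excluded are "Sexually active males unless they use a condom during intercourse while taking azacitidine and for 3 months after stopping the drug". The bars on fathering a child and donating sperm use the same period. Neither venetoclax nor sabatolimab is mentioned.

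**Section 5.2, criterion 17 (women).** Contraception runs "for at least one month after the last dose of venetoclax, 3 months after the last dose of azacitidine". Longer periods in the local labels of those two drugs take precedence, and a sabatolimab period of 150 days is added. All three drugs are named.

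**Section 8.4.3.** Women are again given a three-drug period, "for 90 days after the last dose of azacitidine, 30 days after the last dose of venetoclax" and 150 days after sabatolimab. For men, one stated aim of the condom rule is "to prevent delivery of study treatment via seminal fluid to their partner while taking azacitidine and for 3 months after stopping this drug".

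**Section 7.** Men agree to condom use and not to father a child during the study, plus 3 months after the last azacitidine dose.

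**SAP Section 1.** Recruitment was permanently halted in September 2022 and the expansion part will not open.

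**The concern.** Section 4.6 sends the reader to the exclusion criteria for a requirement that, for men, is not there. The 150 days after sabatolimab appear only in the women's criterion. Men therefore have two post-treatment periods, and nothing in the protocol ranks one section above another. The phrase about the later date in Section 4.6 chooses among the three drugs, not among sections.

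Section 8.4.3 adds to the uncertainty. It describes the purpose in terms of study treatment, which Section 6.1 defines as all three drugs, but ties the duration to azacitidine alone.

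This is a reproductive-safety instruction. Enrolment through the IRT confirms the inclusion and exclusion criteria (Sections 6.3.2 and 8.1.1), so the shorter rule is the one checked at entry. A man who follows criterion 15 or Section 8.4.3 as written can stop before the Section 4.6 period ends. Any consequence might not be seen in the data, because Section 10.1.4 says pregnancy outcomes will not be collected for female partners, although Section 7 lists a partner consent form.

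**Working it through.** The protocol gives no figure for this gap, so there is nothing to reproduce. The check is day arithmetic.

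**Inputs**
- Azacitidine: Days 1-7 of a 28-day cycle, or Days 1-5 and 8-9 (Section 6.1.1). Last dose on Day 7 or Day 9.
- Sabatolimab: Day 8 (Section 6.1.1), which may be delayed by up to 14 days within the cycle (Section 6.5.3).
- Venetoclax: Days 1-14 (Section 6.1.1).
- Any of the drugs may be stopped while the others continue (Section 6.5.3).
- Assumption: 3 months = 90 days. Criterion 17 and Section 8.4.3 write the same azacitidine period for women as 3 months and as 90 days.

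**Formulas.** Day 1 is Day 1 of the last azacitidine cycle. Let k be the number of cycles by which sabatolimab outlasts azacitidine (negative if it stops first), and m the same for venetoclax.
- Criterion 15 end = 7 + 90 = 97 (alternative schedule 9 + 90 = 99).
- Section 4.6 end = the largest of 97 (or 99), 8 + 28k + 150 = 158 + 28k, and 14 + 28m + 30 = 44 + 28m.
- Gap = Section 4.6 end minus criterion 15 end.

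**Results** (m at most 1, so the venetoclax term is at most Day 72 and never decides)

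| Stopping order | Sabatolimab + 150 | Gap, Days 1-7 | Gap, Days 1-5 and 8-9 |
|---|---|---|---|
| Sabatolimab two cycles later (k = 2) | 214 | 117 | 115 |
| Sabatolimab one cycle later (k = 1) | 186 | 89 | 87 |
| Same cycle (k = 0) | 158 | 61 | 59 |
| Same cycle, sabatolimab delayed 14 days (Day 22) | 172 | 75 | 73 |
| Sabatolimab one cycle earlier (k = -1) | 130 | 33 | 31 |
| Sabatolimab two cycles earlier (k = -2) | 102 | 5 | 3 |
| Sabatolimab three cycles earlier (k = -3) | 74 | 0 | 0 |

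**Sensitivity**
- Three calendar months span 89 to 92 days. For the same-cycle case the gap is then 158 - 96 = 62 to 158 - 99 = 59 days.
- The zero in the last row fails if venetoclax outlasts azacitidine by two cycles: 44 + 56 = Day 100, which is 3 days past Day 97.
- The visit window of plus or minus 3 days is not counted.

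**Sabatolimab continued alone.** Section 6.5.3 allows this. The fourth sabatolimab dose after the last azacitidine cycle falls on Day 8 + 4 × 28 = 120, after criterion 15 has expired on Day 97. Read literally, criterion 15 then releases a man who is still being dosed.

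**The case against.** The best counter-reading is that Section 4.6 is a narrative summary which pools both sexes and defers to Section 5.2. On that view the male rule is azacitidine-only. Criterion 15, Section 7 and Section 8.4.3 all tie the male post-treatment period to azacitidine, while Sections 5.2 and 8.4.3 give women a separate three-drug period. That pattern could be deliberate, with Section 4.6 as the outlier. Amendment 1 revisited contraception at health authorities' request and lists a change only to criterion 17. This is plausible, and the documents do not exclude it. But Section 4.6 names men and sets its own end dates, and deferring to criterion 15 cannot supply a 150-day period that criterion 15 lacks. Even if azacitidine-only is intended, the text needs correcting.

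A second point concerns Section 7. Its phrase about the duration of the study could be read to include the 150-day safety follow-up (Section 9.1.1.1). Section 9.2 defines the end of the study and the glossary defines study completion, so the phrase is not wholly without an anchor. Section 7 does not say which of these is meant, however, and neither reading changes criterion 15 or Section 8.4.3.

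Three limits on importance stand. The rules can all be met by following the longest. The consent form is not among the documents and may already settle the matter. Recruitment has stopped, and the documents do not say how many treated men, if any, are still within a window.

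**Conclusion.** The inconsistency is real. Section 4.6 and the pair formed by criterion 15 and Section 8.4.3 set different end dates for men, and nothing in the protocol resolves them. The gap is 61 days if all drugs stop in the same cycle on the standard schedule with 3 months taken as 90 days. It ranges from zero to more than 100 days with the order of stopping. The documents give no distribution of stopping orders, so no case is put forward as typical.

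Which rule the sponsor intended cannot be determined from the protocol. Differing site practice is a risk and has not been shown. The reach is limited to men in the safety run-in, planned at about 18 participants of both sexes. No endpoint, sample size or analysis is affected. It should still be corrected, because it is a conflicting safety instruction and the remedy is cheap.

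**What to change.** State one male window in identical words in Sections 4.6, 5.2 (criterion 15), 7 and 8.4.3, covering condom use, fathering a child and sperm donation.

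- **Protective default:** during any study treatment and until the latest of 30 days after the last venetoclax dose, 90 days after the last azacitidine dose and 150 days after the last sabatolimab dose. In the same-cycle case this moves the end of criterion 15 from Day 97 to Day 158 and closes the gap.
- **If the sponsor confirms that an azacitidine-only rule is intended for men:** remove males from the Section 4.6 sentence, correct the reference to study treatment in the men's paragraph of Section 8.4.3, and say in Section 7 when the study period ends for this purpose.

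In either case, check the consent form against the chosen window and tell sites which window applies to men already treated. The cost is a wording change or clarification letter, one consent-form check and a site notice. If every treated man is already past the longer period, only the wording correction remains.

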6.1 Study treatment

In this study, the term "investigational drug" refers to the Novartis study drug, sabatolimab. The term "study treatment" refers to the combination of study drugs: sabatolimab plus venetoclax plus azacitidine.

All dosages prescribed, dispensed to the participant and all dose changes during the study including the reason for any component of the study treatment must be recorded on the appropriate eCRF page.

6.1.1 Investigational and control drugs

Investigational/ Combination Drug (Name and Strength)	Strength	Pharmaceutical dosage form and route of administration	Supply Type	Sponsor (global or local)
Sabatolimab	400 mg/4 ml	solution in vial for i.v. infusion	solution in vial Open Label for i.v. infusion	
Venetoclax	100 mg and/or 50 mg and/or 10 mg	tablet for oral use	Open Label	Sponsor (global/local)
Azacitidine*	100 mg / vial	powder for suspension for injection or powder for solution for infusion for subcutaneous use or intravenous use	Open Label	Sponsor (global/local)

Table 6-1Study Treatment

*formulation for generic azacitidine as approved by local regulations

Sabatolimab

Sabatolimab will be administered at a dose of 400 mg Q4W (Safety run-in (Part 1) cohort 1) or 800 mg Q4W (Safety run-in (Part 1) cohort 2 and Expansion (Part 2)) via i.v. infusion over 30 minutes on Day 8 of every 28-day cycle.

If the alternative schedule is selected for azacitidine by the investigator, azacitidine and sabatolimab will be given on the same day (Day 8 of the 28-day cycle). Azacitidine should be administered first, followed by sabatolimab.

Further instructions for the preparation, dispensation and administration of sabatolimab are described in the Pharmacy Manual.

Venetoclax

Venetoclax film-coated tablets should be administered at a dose of 400 mg orally or corresponding reduced dose for concomitant use with P-gp inhibitors or moderate or strong CYP3A4 inhibitors (see Table 6-2 and Venclexta[®] (Venclexta[®] (Venetoclax) USPI (2020)), once a day, from C1D1 to C1D14 during the 28-day cycle. Participants should be instructed to

swallow the tablets whole (tablets should not be crushed or broken), with water, at approximately the same time each day. The tablets should be taken with a meal (ideally at breakfast). No ramp-up for venetoclax is necessary, See Section 3, Section 4.3 and Section 6.5.4.2.

A reduced dose of venetoclax per day for concomitant use with P-gp inhibitors or moderate or strong CYP3A4 inhibitors (see Table 6-2 and Venclexta[®] (Venclexta[®] (Venetoclax) USPI (2020)) is necessary. In particular, many antifungals (e.g. posaconazole) and antibiotics, frequently used for prophylaxis or treatment of infection, are strong or moderate CYP3A4 inhibitors and their use should lead to dose adjustment of venetoclax as indicated in Table 6-2.

If a participant misses doses of venetoclax within 8 hours of the time it is usually taken, the participant should take the missed dose as soon as possible on the same day. If the participant misses a dose by more than 8 hours, the participant should not take the missed dose and should resume the usual dosing schedule at the usual time the following day. If a participant vomits after taking venetoclax, the dose should not be re-administered and the participant should take their next dose at the usual time the following day.

On the days of PK sampling, the participant will be instructed to bring his/her drug supply to the site, and take the dose in the clinic, under supervision of the site personnel. The exact time for dose administration and breakfast (if applicable) intake must be recorded in the source documents and electronic Case Report Form (CRF).

Azacitidine

Azacitidine is considered as a Standard of Care in the population enrolled in this study and it should be administered according to standard local clinical practice. A standard dose of azacitidine (75 mg/m²) will be given subcutaneously or intravenously every day for seven consecutive days on days 1-7 out of a 28 days cycle (see local azacitidine package insert). In keeping with standard clinical practice, the alternative schedules of 75 mg/m² for five consecutive days on days 1-5, followed by a two day break, then two consecutive days on days 8-9 will be permitted (alternative schedule).

Azacitidine regimen used in this protocol were selected because they are the most studied regimens and recommended by international treatment guidelines (NCCN, ESMO) (Fey and Buske 2013, O'Donnell et al 2017).

NOTE: On days of co-administration of venetoclax, azacitidine and sabatolimab, please refer to the Pharmacy Manual for instructions.

6.1.2 Additional study treatments

No other treatment beyond investigational drug and control drug are included in this trial.

6.1.3 Treatment arms/group

Not applicable.

6.1.4 Guidelines for continuation of treatment

Per protocol, dose modifications, including dose interruptions, for toxicities are permitted and are outlined in Section 6.5.

6.1.5 Treatment duration

A participant may be discontinued from study treatment for reasons of unacceptable toxicity, progressive disease (including transformation to leukemia per WHO 2016 classification) or relapse, HSCT, intensive chemotherapy, withdrawal of consent by the participant, pregnancy, failure to adhere the protocol or at the discretion of the investigator or if the study is terminated by the Sponsor.

Patients who complete participation in this trial and continue to derive clinical benefit from the treatment based on the investigator's evaluation may receive post-trial access. Post Trial Access (PTA) means the provision of investigational treatment to trial participants following their completion of trial participation. PTA will be provided until one of the following is met: participant no longer derives clinical benefit, investigator discontinues treatment, launch or reimbursement (where applicable), treatment fails to achieve registration in the trial participant's country, or the clinical program is discontinued for any other reason.

Mechanisms for provision of PTA may include an extension phase to this study, a separate extension protocol, a rollover protocol, provision of the Novartis investigational product in a non-trial setting (known as post-study drug supply [PSDS]) when no further safety or efficacy data are required, or any other mechanism appropriate for the country.

The PTA mechanism must comply with local laws and regulations in the participating trial countries. If Novartis discontinues the PTA for this trial, Novartis will work with investigators to transition patients onto locally available alternative treatment, or standard of care.

6.1.5.1 Treatment beyond disease progression

Treatment beyond disease progression is not permitted.

6.2 Other treatment(s)

6.2.1 Concomitant therapy

In general, the use of any concomitant medication/therapy deemed necessary for the care of the participant (e.g., such as antibiotics, antifungals, anti-emetics, anti-diarrheal) is permitted (see Section 6.2.1.1), except when specifically prohibited (see Section 6.2.2). Prophylaxis with antibiotics as per local institutional guidelines is mandatory at Cycle 1 and thereafter this type of prophylaxis may be used per investigator's discretion. Prophylaxis antifungals, as per institutional guidelines, is allowed at anytime. In case of concomitant medications (e.g antibiotics, antifungals), dose adjustment of venetoclax may be necessary, as indicated below. The participant must be told to notify the investigational site about any new medications he/she takes after the start of the study treatment.

Participants should not receive pre-medication to prevent infusion reaction before the first infusion of sabatolimab. If a participant experiences an infusion reaction, he/she may receive

pre-medication on subsequent dosing days. The pre-medication should be chosen per institutional standard of care, at the discretion of the treating physician.

Acute allergic reactions should be treated as needed per institutional standard of care. In the event of anaphylactic/anaphylactoid reactions, this includes any therapy necessary to restore normal cardiopulmonary status. If a participant experiences a Grade ≥ 3 anaphylactic/anaphylactoid reaction, the participant will be discontinued from the study treatment (see Section 6.5.3 for guidance).

Sabatolimab should be administered in a facility equipped for cardiopulmonary resuscitation. Appropriate resuscitation equipment should be available, and a physician readily available.

Participants should receive appropriate prophylaxis (e.g. antiemetics) for azacitidine as per local practice.

All medications, procedures, and significant non-drug therapies including physical therapy and blood transfusions received within 16 weeks before the first dose of study treatment is administered, during the course of the study and until the end of efficacy follow-up, should be recorded in the appropriate Case Report Forms (see Table 8-1).

Each concomitant drug must be individually assessed against all exclusion criteria/prohibited medications and local prescribing information of azacitidine (Vidaza® (Azacitidine) USPI (2008)) and venetoclax (Venclexta® (Venetoclax) USPI (2020)). If in doubt, the investigator should contact the Novartis medical monitor before a participant starts treatment or allowing a new medication to be started. If the participant has already started treatment, contact Novartis medical monitor to determine if the participant should continue study treatment. Supportive therapy including prophylactic antibiotic and antifungal treatments, transfusions, growth factors (e.g. GCSF, ESA) etc. will be administered at the discretion of the investigators according to their local standard of care.

